8.2. Setting

Population

This study will use data from a large, commercially available, database of adjudicated medical and pharmacy claims from closed-network health insurers in the US. The population in this database is broadly representative of those in the US covered by commercial, managed Medicare, or managed Medicaid health plans⁴⁰.

Care setting

Medical claims in this database represent all care settings (e.g., physician office, hospital outpatient, hospital inpatient) and all health care provider services (e.g., evaluation and management, diagnostic procedures, nonsurgical procedures, surgical procedures) commonly reimbursed by third-party payers. Pharmacy claims in this database are primarily from retail pharmacies.

Time period

The study will examine data from September 1, 2019, to March 31, 2023. The first date of rimegepant initiation during this period will be defined as the index date.

The pattern of opioid and barbiturate utilization will be assessed 180 days before (pre-index) and 180 days after (post-index) the index date. The study baseline will be defined as the pre-index period plus the index date. Each outcome measure will be calculated separately for 12 consecutive 30-day periods (study months), starting 6 months before and ending 6 months after the index date.

Baseline clinical characteristics and comorbidities will be assessed based on diagnosis codes in inpatient or outpatient medical claims. Medication use will be identified from National Drug Codes (NDC) in pharmacy claims or Healthcare Common Procedural Coding System (HCPCS) codes in medical claims. Migraine medications will be categorized as those intended for acute treatment, prevention of, or both, based on their common usage for migraine.

8.2.1. Inclusion Criteria

Patients must meet all of the following inclusion criteria to be eligible for inclusion in the study:

- 1. Have an index ("first") prescription fill for rimegepant between March 1, 2020, and October 1, 2022; the date of this index fill defines the index date
 - a. The end date of cohort eligibility is 6 months prior to the end of data availability to ensure sufficient follow-up for all patients prior to the end of data availability. For the 12-month sensitivity analysis, the end of cohort eligibility will be April 1, 2022.
- 2. Have an index fill quantity for rimegepant of 8 tablets (ie, intended use for acute treatment of migraine).
- 3. Have ≥ 180 days of rimegepant use from index date to last fill date +30 days
 - a. The period of rimegepant use is measured as the number of days from the index date, or first observed rimegepant fill, to the last observed rimegepant fill date +30 days.
- 4. Be \geq 18 years of age on the index date

- 5. Have ≥180 days of continuous enrollment in commercial health plans with both medical and pharmacy benefits prior to and following the index date, defined as the pre-index period and post-index period, respectively
- 6. Have a diagnosis of "migraine" (ICD-10-CM code: G43.xx) at *any point* during the pre- or post-index periodsHave ≥1 prescription fill during the pre-index period for one of the following drugs of interest: opioids, barbiturates (butalbital), alprazolam, rescue inhalers, or statins

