7. RESEARCH QUESTION AND OBJECTIVES

The study aims to address the following research question: Among US adults with migraine and prior use of opioids or barbiturates, how does the use of opioids and barbiturates change following rimegepant initiation? Specific study objectives include:

Primary Objective

1. To evaluate changes in opioid and barbiturate utilization patterns after the initiation of rimegepant.

Secondary Objectives

- 2. To describe the pre-treatment characteristics of new rimegepant users, including demographics, comorbid conditions, and prior medication use.
- 3. To evaluate changes in opioid and barbiturate utilization patterns after the initiation of rimegepant in the subset of individuals using at least one preventive treatment for migraine
- 4. To evaluate changes in opioid and barbiturate utilization patterns after the initiation of rimegepant in the subset of individuals with problematic opioid use (≥ 3 opioid prescriptions and/or morphine milligram equivalents [MME] above 75th percentile during pre-index period)

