This study design is appropriate to the study objectives and allows for the evaluation of real-world prescription medication use patterns in a large group of individuals broadly representative of patients in the US taking rimegepant without influencing patient or provider behavior. Pharmacy claims databases are often used for this purpose, supplemented by medical claims to provide diagnosis codes to help understand why medications are being used and the comorbidities of individuals taking those medications^{41,42}. By utilizing an administrative claims database, the study can efficiently examine the use of prescription medications dispensed by retail pharmacies and similar outlets in a large and diverse population of adults in the US with commercial health plans^{42,43}.

The pre- vs. post- study design is commonly used in non-interventional studies using real world data and allows researchers to examine outcomes of interest before and after an event occurs⁴⁴. Such study designs are unable to establish a causal relationship between the event and outcome and researchers must be cautious to minimize bias and confounding. The use of multiple control groups for medications intended for continuous or episodic use (alprazolam, rescue inhalers, statins) provides relevant comparators and enhances the validity of the findings observed. Study findings might inform future studies focused on how the use of rimegepant for migraine might impact the use of other, suboptimal medications (opioids/barbiturates) often used for migraine.

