11. Because rimegepant has 2 approved indications with different dosing regimens, assumptions must be made about its intended use based on the quantity of tablets dispensed (ie, 8 tablets = acute treatment, 16 tablets = prevention). It's possible that some individuals who received 16 tablets of rimegepant were using it for the acute treatment of migraine, resulting in the misclassification and exclusion of otherwise eligible individuals from our study population. However, the likelihood of this occurring seems low since most individuals using rimegepant for the acute treatment of migraine use only 2-5 tablets/month.⁵⁴.

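### Inclusion criterion 3 limits the cohort to initiators who fill rimegepant on or after day 150, so the before-after result does not describe all initiators and may overstate the reduction

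*Protocol*

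**What the plan says.** Section 7 asks "how does the use of opioids and barbiturates change following rimegepant initiation", and the abstract defines the exposure as the first fill. Section 8.2 measures outcomes over 180 days before and 180 days after that fill.

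Among the entry conditions in section 8.2.1 is criterion 3: "Have ≥ 180 days of rimegepant use from index date to last fill date +30 days". Item 3a measures the period from the first observed fill "to the last observed rimegepant fill date +30 days". It states no maximum gap, no minimum number of fills and no cut-off at day 180. Criterion 1 accepts a first "prescription fill for rimegepant between March 1, 2020, and October 1, 2022". Section 8.2 sets the data window: "The study will examine data from September 1, 2019, to March 31, 2023". Criterion 5 sets a minimum for enrolment and no maximum: "Have ≥180 days of continuous enrollment in commercial health plans with both medical and pharmacy benefits prior to and following the index date".

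Section 8.1 describes the individuals studied as "broadly representative of patients in the US taking rimegepant". Section 8.9, item 11, says that "most individuals using rimegepant for the acute treatment of migraine use only 2-5 tablets/month". None of the listed limitations mentions the refill requirement.

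**The concern.** The study asks what happens after patients start rimegepant, but entry depends on what they do about five months later or beyond. Patients who try the drug and stop are left out, and they may include those who keep using, or return to, opioids or butalbital. If patients who benefit refill more often, the cohort is enriched for benefit and its pre-to-post change looks larger than the change among everyone who started.

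Nothing else in the plan deals with this. The model covariates in section 8.7.1 are all pre-index. The two sensitivity analyses lengthen the windows to 360 days or exclude surgery and injury; neither relaxes criterion 3. The alprazolam, inhaler and statin groups pass the same filter, but their use has no evident link to migraine response, so a flat result there would not rule out selection in the opioid and butalbital groups.

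There is a second problem. A span from first to last observed fill is not a measure of persistence, and how easily it is met depends on how long the patient can be observed.

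**Working it through.** **Plan's own figure.** Section 8.5 gives 4,049 eligible of 52,591,063: 4,049 / 52,591,063 = 0.0077%, which reproduces. Of the 45,051 with an eligible first prescription, 4,049 / 45,051 = 9.0% remain after all criteria together. Attrition by criterion is not given, so criterion 3's share cannot be derived.

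**What criterion 3 requires.** Last fill day + 30 ≥ 180, so last fill day ≥ 150. Fills on day 0 and day 150 pass. So do fills on day 0 and, say, day 700 for an early initiator who remains observed, although no refill falls in the 180-day outcome window.

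**Qualifying window by index date.** Data end on 31 March 2023. Window = follow-up − 150 + 1 days.

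| Index date | Maximum follow-up (days) | Qualifying days | Length (days) |
|---|---|---|---|
| 1 Mar 2020 | 1,125 | 150-1,125 | 976 |
| 1 Apr 2022 | 364 | 150-364 | 215 |
| 1 Oct 2022 | 181 | 150-181 | 32 |

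976 / 32 is about 30-fold. These lengths are maxima, because they need enrolment to continue to the end of data. With a cap at day 180 the window would be 31 days (150-180) for everyone.

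**Uninterrupted users at 2-5 tablets/month.** Pack duration = 8 / rate × 30 days. For index 1 October 2022 (follow-up 181 days):

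| Tablets/month | Pack lasts (days) | Fills by day 181 | Last fill + 30 | Criterion 3 |
|---|---|---|---|---|
| 2 | 120 | 0, 120 | 150 | fails |
| 3 | 80 | 0, 80, 160 | 190 | passes |
| 4 | 60 | 0, 60, 120, 180 | 210 | passes |
| 5 | 48 | 0, 48, 96, 144 | 174 | fails |

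The next fill is day 192 at 5/month and day 240 at 2/month. Those days fall within the data if the index date is no later than 20 September 2022 and 3 August 2022 respectively. The excluded index dates are therefore the last 11 days (5/month) and the last 59 days (2/month) of a window of about 31 months.

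**Illustration of date dependence (assumed constant fill rate, enrolment to end of data).** P(qualify) = 1 − exp(−rate × window / 30). At one fill per 90 days (rate 1/3 per 30 days), it is 1.00 for index 1 March 2020 and 1 − exp(−32/90) = 0.30 for index 1 October 2022.

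**Illustration of selection (all values assumed).** Half of initiators respond with a 30% fall in opioid use and half do not change, so the mean over all initiators is −15%.
- If 60% of responders and 20% of non-responders refill past day 150, the responder share in the cohort is 0.30 / (0.30 + 0.10) = 0.75 and the cohort shows 0.75 × −30% = −22.5%.
- At 40% versus 10%, the share is 0.20 / 0.25 = 0.80 and the cohort shows −24%.
- With equal refill rates the cohort shows −15%, so there is no bias.

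**The case against.** A population of continuing users is a legitimate target if it is labelled as one, and replacing the primary cohort is a debatable remedy: the abstract says analyses were completed in 2024 and a manuscript was accepted in 2025. This stands, and it is why the fix adds an analysis and does not substitute one.

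The direction of bias can be disputed. Outcomes are fills for any reason (section 8.4), so many may have nothing to do with migraine. Refilling could also mark more frequent attacks, which might work the other way. This stands too: the documents support a possible overstatement, not a demonstrated one.

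The failing examples are narrow. Users at 3 and 4 tablets/month pass even on the last eligible date. The sensitivity analysis with 360-day windows ends eligibility on 1 April 2022, which leaves at least 364 days of data. If criterion 3 stays at 180 days there, all four example users qualify. This largely answers the late-initiator exclusion but leaves the main selection untouched. A reader might also infer that the 30-day tail contradicts the 2-5 tablets/month figure. It does not, because section 8.2.1 never says a pack lasts 30 days; the tail may simply be short for these users.

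Finally, section 8.6 places operational definitions in a data dictionary that is not at hand, and a cap might be stated there. The criticism is therefore that the protocol states none.

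**Conclusion.** The point holds as a mismatch between the stated question and the cohort. Criterion 3 selects initiators on a rimegepant fill at day 150 or later. The protocol neither discloses this as a limitation nor tests it, and its claim of representativeness does not fit the selected group. As written, the rule also makes the chance of entry depend on index date, with a potential window of 32 to at most 976 days, and it admits patients with as few as two fills.

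Three stronger readings do not follow:
- A reader might infer that the cohort is not made up of initiators. It is: every patient enters at a first fill. They are a selected subset.
- A reader might infer that the reduction is inflated by a known amount. The −22.5% and −24% figures rest on assumed response and refill rates, and equal refill rates give no bias.
- A reader might blame criterion 3 for the drop to 9.0%. That figure also reflects the 8-tablet quantity, age, enrolment, migraine diagnosis, prior drug use and the exclusions.

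The number of patients without criterion 3 can only be bounded, between 4,049 and 45,051.

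**What to change.** 1. Report the same analysis in all initiators who meet the other criteria, beside the criterion-3 cohort, with attrition by criterion.
2. Assess persistence only from fills within days 0-180, with a stated maximum gap compatible with 2-5 tablets/month (packs lasting 48 to 120 days). The two parts belong together: a cap alone, with the 30-day tail kept, would fail the 2/month and 5/month users above at every index date (150 and 174 against 180).
3. Describe the criterion-3 result as applying to patients still filling rimegepant at about 6 months.
4. Correct the representativeness statement in section 8.1 and add this selection to section 8.9.

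Cost: section 8.6 plans a single extract limited to eligible patients, so a further extract is needed, assuming the data licence still allows it, plus one more run of the programs. The added analysis must be labelled post hoc, since results already exist. The final study report is planned for 1 March 2026 (section 5), so the wording changes and the added analysis can be placed there.

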8.2.2. Exclusion Criteria

Patients meeting any of the following criteria will be excluded from the study:

- 1. Prior use of other novel agents for acute treatment of migraine (i.e., ubrogepant or lasmiditan) in the pre-index period
- 2. Diagnosis of malignant neoplasm (cancer) during the pre or post-index periods

8.3. Variables

The study variables and its operational definition are listed in Table 1.

Table 1. Variables description

Variable	Role	Data source(s)	Operational definition			
	Demographic characteristics					
Age	Baseline characteristic	Enrollment files	Continuous: Mean/SD			
Age categories	Baseline characteristic	Calculated	Categorical: 18-34, 35-54, 55-64, 65+			
Age 55 category	Baseline characteristic	Calculated	Categorical: 18-54, 55+			
Sex	Baseline characteristic	Enrollment files	Categorical: Male, Female, Unknown			
Region	Baseline characteristic	Enrollment files	Categorical: Northeast, South, West, Midwest			
I	Prior migraine treatm	ents during pre-index	period			
Triptans	Baseline characteristic	Rx claims	Binary (any use)			
Ergotamines	Baseline characteristic	Rx claims	Binary (any use)			
NSAIDs	Baseline characteristic	Rx claims	Binary (any use)			
Acetaminophen	Baseline characteristic	Rx claims	Binary (any use)			

		1	T
Beta blockers	Baseline characteristic	Rx claims	Binary (any use)
Tricyclic antidepressants	Baseline characteristic	Rx claims	Binary (any use)
Antidepressants	Baseline characteristic	Rx claims	Binary (any use)
Anticonvulsants	Baseline characteristic	Rx claims	Binary (any use)
Anti-CGRP monoclonal antibodies	Baseline characteristic	Rx and medical (HCPCS) claims	Binary (any use)
Onabotulinumtoxin A	Baseline characteristic	Rx and medical (HCPCS) claims	Binary (any use)
Isometheptene combinations	Baseline characteristic	Rx claims	Binary (any use)
Antiemetics (migraine)	Baseline characteristic	Rx claims	Binary (any use)
Antiemetics (other)	Baseline characteristic	Rx claims	Binary (any use)
Used ≥1 conventional oral prevention agent during pre-index	Baseline characteristic	Calculated	Binary (any use)
Used ≥1 of any prevention agent during pre-index	Baseline characteristic	Calculated. Includes the above variable + anti-CGRP mabs + onabotulinumtoxinA	Binary (any use)
	Comorl	oid conditions	
Elixhauser comorbidities	Baseline characteristic	Medical claims	Binary
Elixhauser weighted index	Baseline characteristic	Calculated	Discrete
Elixhauser index categories	Baseline characteristic	Calculated	Categorical: 0, 1, 2-3, 4-5, ≥6
Other chronic pain	Baseline characteristic	Medical claims	Binary (ICD-10)
Chronic migraine	Baseline characteristic	Medical claims	Binary (ICD-10)
Any chronic pain (includes chronic migraine + other chronic pain)	Baseline characteristic	Calculated	Binary

Any injury	Baseline characteristic	Medical claims	Binary (ICD-10)	
Any surgical procedure	Baseline characteristic	Medical claims	Binary (CPT)	
	Outcon	ne Measures		
Total number of fills dispensed	Outcome measure	Rx claims	Count	
Total quantity dispensed	Outcome measure	Rx claims	Count	
Average dose (MME or mg) within time period	Outcome measure	Calculated	Continuous (calculated): Mean/SD	
Total duration of use (days)	Outcome measure	Calculated	Continuous (calculated)	
Discontinuation	Outcome measure	Rx claims	Binary (no prescription fills during post-index period)	
Additional measures for opioid use group:				
Type of opioid used	Outcome measure	Rx claims	Binary	
Total number of Rx opioid agents used (mean)	Outcome measure	Rx claims	Count	
Total number of Rx opioid agents used	Outcome measure	Rx claims	Categorical: $1, 2, \ge 3$	

CGRP: Calcitonin Gene-Related Peptide; CPT: Current Procedural Terminology; HCPCS: Healthcare Common Procedural Coding System; ICD10: International Classification of Diseases, 10th Revision; MME: Morphine Milligram Equivalents; NSAIDs: Nonsteroidal anti-inflammatory drugs; Rx: Prescription; SD: Standard Deviation

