8. RESEARCH METHODS

8.1. Study Design

This is a non-interventional, retrospective, observational, cohort study that will assess changes in opioid and barbiturate utilization after initiation of rimegepant among adults in the US. This study will analyze an administrative claims database (IQVIA PharMetrics® Plus) with information on

individuals in the US with commercial, managed Medicare, or managed Medicaid health plans. This database includes information captured in medical and pharmacy claims (e.g., dates of service, diagnosis codes, procedure codes, medications dispensed, demographics, health plan enrolment)⁴⁰.

This study aims to characterize, in a real-world setting, the use of opioids and barbiturates among individuals with migraine before and after initiating rimegepant. Individuals will be grouped according to their use of 5 medications prior to rimegepant initiation (index date): 1. opioids, 2. barbiturates (i.e., butalbital), 3. alprazolam, 4. rescue inhalers, or 5. statins. The latter three groups will be used as controls to represent medications intended for continuous use and episodic use.

Rimegepant is approved for both the acute treatment of migraine and the prevention of episodic migraine. For the acute treatment of migraine, rimegepant is taken as needed. For the prevention of episodic migraine, rimegepant is taken every other day. Since the same medication is approved for 2 indications, assumptions must be made about the intended use when analyzing real world data.

Rimegepant is commonly dispensed in packages of 8 tablets. When 2 packages (16 tablets) are dispensed, it is assumed that rimegepant is intended for the prevention of episodic migraine. When 1 package (8 tablets) are dispensed, it is assumed that rimegepant is intended for the acute treatment of migraine.

For each medication of interest, outcome measures will include the total number of prescriptions filled/dispensed, the total quantity dispensed (number of tablets or other medication units), the average dispensed per fill (calculated for opioids in MME and for butalbital and alprazolam in mg), the total duration of use (days supplied), and the proportion of individuals with discontinuation (defined as the absence of any prescription fill in after rimegepant initiation).

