8.7.1. Statistical analysis plan

- 1. Among each medication use group, a report with descriptive statistics of the demographic and clinical baseline characteristics as well as medication use prior to rimegepant will be created.
- 2. Next, a patient-level dataset containing crude counts of the five utilization outcome measures for each 30-day window (W1-W12) of the pre- and post-index periods will be created.
- 3. To measure changes in utilization outcome measures across the pre-index to post-index period, two aggregated measures for each outcome based on time during the pre- (W1-W6) or post-index (W7-W12) period will be created. Using these aggregate measures, the pre and post-index mean outcome values and determine the percent change (%Δ) will be presented.
- 4. In order to determine the association between rimegepant initiation and reduction of other acute treatments, a generalized linear mixed models for each outcome will be applied. Mixed effects models account for within-person correlation due to the repeated measurement of outcomes over time in longitudinal studies. The main independent (exposure) variable will be a binary indicator of time during the pre-index period (0) vs. post-index period (1). For modeling the continuous and count outcomes—number of fills, quantity dispensed, average dose, and duration of use—first the distribution of each utilization outcome measure within the dataset will be determined in order to specify the appropriate distributions and link functions for their mixed model. The discontinuation outcome is a binary outcome, observed at one point in time. Hence, a logistic regression model to examine any association to rimegepant initiation will be applied. For each model, for pre-index demographic and clinical characteristics, including age, sex, region, presence of any chronic pain (migraine or non-migraine), Elixhauser weighted index, and pre-index use of any prevention agent will be adjusted.
- 5. To determine the robustness of the outcome measures and association estimates, two subgroups and two sensitivity analyses will be performed as described below. The sensitivity analyses only apply to the total cohort, and not the additional subgroups.
 - a) Subgroup analysis #1: Identify all individuals from the total cohort with use of ≥ 1 prevention agent during the pre-index period, presented by medication use group.

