- b) Subgroup analysis #2: Identify individuals form the opioid use group having potentially problematic opioid use. This subgroup is a composite of problematic opioid use defined in two ways. Patients meeting either measurement definition will be included.
 - i. The first method will identify individuals in the cohort with ≥ 3 opioid prescriptions during the pre-index period.
- 6. The second method will calculate quartiles of opioid dose in MMEs and identifies individuals within the fourth quartile (76th to 100th percentile) during the pre-index period.
 - c) Sensitivity analysis #1: Increase the duration of the pre-index and post-index periods from 180 days each to 360 days each.
 - d) Sensitivity analysis #2: Exclude all patients having a major surgical procedure or injury diagnosis at any point during the study period.

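### Discontinuation is scored as no fill in the 180 days after index with no requirement of recent use before it, so earlier lapses and chance gaps count as stopping after rimegepant

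*Protocol*

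**What the plan says.** The outcome is defined twice in the Protocol, in the same way. Section 8.1 lists "the proportion of individuals with discontinuation (defined as the absence of any prescription fill in after rimegepant initiation" among the five utilization measures. Table 1 in Section 8.3 gives the operational definition as "Binary (no prescription fills during post-index period".

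Entry to a medication group is set in Section 8.2.1: "≥1 prescription fill during the pre-index period for one of the following drugs of interest". Section 8.1 describes the grouping only by prior use: "Individuals will be grouped according to their use of 5 medications prior to rimegepant initiation (index date". The windows come from Section 8.2: "The pattern of opioid and barbiturate utilization will be assessed 180 days before (pre-index) and 180 days after (post-index) the index date".

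For analysis, Section 8.7.1 step 4 says "The discontinuation outcome is a binary outcome, observed at one point in time" and applies a logistic regression to examine any association with rimegepant initiation. Steps 2 and 3 build a patient-level file of twelve 30-day windows, W1-W6 before index and W7-W12 after.

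No section shown asks for a recent fill, for supply reaching the index date, or for a second fill.

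**The concern.** The entry rule is one or more fills in 180 days and the outcome rule is zero fills in the next 180 days. A patient can pass from one to the other by a difference of a single fill, and the fill that qualified the patient may lie at the far end of the pre-index window. Someone with one 5-day opioid fill 170 days before index and none since is scored as discontinuing after rimegepant, although the supply ran out more than five months earlier.

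Two kinds of patient enter the numerator without having stopped after initiation: those whose use had already ended, and those who fill rarely and happen to have no fill in one half-year. Discontinuation is one of the five measures for the primary objective, and the plan ties it to rimegepant initiation. If much of it arises from the scoring rule, it will be read as evidence that it cannot carry.

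**Working it through.** The protocol states no discontinuation rate, fill rate or power, so there is no figure of its own to reproduce. The windows and the entry and outcome rules come from Sections 8.1 to 8.3 and 8.7.1. All fill rates and days supplied below are assumptions.

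**1. Stable use, no drug effect.** Let a patient's fills be Poisson with a constant personal rate, and let rates vary between patients as a gamma distribution with mean m per 180 days and shape k. The probability of no fill over t half-years is P0(t) = (1 + m·t/k)^(-k). Then:

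- A, present rule: P(no fill in W7-W12, given at least one in W1-W6) = [P0(1) − P0(2)] / [1 − P0(1)]
- B, entrants with no W4-W6 fill: [P0(0.5) − P0(1)] / [1 − P0(1)]
- C, at least one fill in W4-W6, same 180-day outcome: [P0(1) − P0(1.5)] / [1 − P0(0.5)]
- D, at least one fill in W4-W6, no fill in W7-W9: [P0(0.5) − P0(1)] / [1 − P0(0.5)]

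Example, m = 1 and k = 1, so P0(t) = 1/(1 + t): A = (0.500 − 0.333)/0.500 = 0.333; B = (0.667 − 0.500)/0.500 = 0.333; C = (0.500 − 0.400)/0.333 = 0.300; D = (0.667 − 0.500)/0.333 = 0.500.

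| m | k | A | B | C | D |
|---|---|---|---|---|---|
| 0.5 | 0.3 | 0.396 | 0.348 | 0.351 | 0.533 |
| 0.5 | 0.5 | 0.443 | 0.373 | 0.407 | 0.596 |
| 0.5 | 1.0 | 0.500 | 0.400 | 0.476 | 0.667 |
| 1 | 0.3 | 0.285 | 0.284 | 0.235 | 0.396 |
| 1 | 0.5 | 0.308 | 0.307 | 0.264 | 0.443 |
| 1 | 1.0 | 0.333 | 0.333 | 0.300 | 0.500 |
| 2 | 0.3 | 0.203 | 0.222 | 0.157 | 0.285 |
| 2 | 0.5 | 0.206 | 0.235 | 0.164 | 0.308 |
| 2 | 1.0 | 0.200 | 0.250 | 0.167 | 0.333 |

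With no drug effect, the present rule scores 20% to 50% as discontinued. Requiring a W4-W6 fill and keeping the 180-day outcome gives 16% to 48%, lower in every setting but far from zero. Shortening the outcome to 90 days (D) raises the proportion to 28% to 67%, so a shorter outcome window is not a good replacement.

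**2. One-off users.** This is where true lapse enters. Take a single fill at a uniformly distributed date in the 180 days, with d days supplied and no later fill. Every such patient is scored as discontinued. The share whose supply ended before index is 1 − d/180: 97% for d = 5, 94% for d = 10, 83% for d = 30. If, say, 25% of a group were such users, those already lapsed would make up 0.25 × 0.833 = 21% (d = 30) to 0.25 × 0.944 = 24% (d = 10) of the group.

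**3. Do the control drugs calibrate this?** With a common constant rate λ per 180 days, the no-effect proportion is exp(−λ): 37% at 1 fill, 14% at 2, 0.2% at 6. The artefact depends on how often a drug is filled. A regularly filled control shows almost none of it.

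**4. An earlier step as benchmark.** Under stable use, W1-W3 users with no W4-W6 fill have the same expected proportion as W4-W6 users with no W7-W9 fill; both equal column D. This fails if use rises just before index. With m = 1, k = 0.5, the W4-W6 rate multiplied by r and use then returning to usual:

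- step across index = [P0(0.5) − P0(0.5 + 0.5r)] / [1 − P0(0.5r)]
- earlier step = [P0(0.5r) − P0(0.5 + 0.5r)] / [1 − P0(0.5)]

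At r = 1.25 these are 0.457 and 0.382, a gap of 7.5 points. At r = 2 they are 0.490 and 0.264, a gap of 22.6 points. Both gaps arise with a drug that does nothing.

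**The case against.** The plan has partial safeguards. Section 8.1 says "The latter three groups will be used as controls to represent medications intended for continuous use and episodic use", and Table 2 tabulates discontinuation for all five drugs. Sensitivity analysis #2 is to "Exclude all patients having a major surgical procedure or injury diagnosis at any point during the study period", which should remove some one-off opioid courses. Subgroup #2 includes patients with three or more opioid fills, sensitivity analysis #1 lengthens the windows to 360 days, and Sections 8.1 and 8.9 disclaim causal attribution. These reduce the problem or warn about it, but none sets a condition of use near index. The controls are scored by the same rule, no between-group test of discontinuation is described, and a contrast with a regularly filled drug such as a statin could exaggerate an apparent effect. Subgroup #2 covers opioids only and can be entered on MME alone.

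Section 8.6 places the outcome algorithms in a data dictionary that is not shown, and it may hold an active-use rule. That is possible, but the protocol gives its own definition twice without one.

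Three stronger readings are tempting and not supported:

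- A reader might take the 20% to 50% as the share who had lapsed before rimegepant. In that model nobody stops; the figure is chance zero counts after selection on at least one fill.
- A reader might call it an error that a patient who fills on day 3 after index and never again counts as continuing. That follows the stated rule, lowers the proportion, and is not a misclassification under stable as-needed use.
- A reader might say that every lapsed patient is miscounted. One who refills after index is not.

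**Conclusion.** The concern holds on the protocol's text. The measure is the proportion with no post-index fill among patients with at least one pre-index fill; it is not the proportion stopping after rimegepant. Its no-effect value is not zero. It is 20% to 50% under the assumed stable gamma-Poisson model, and one-off users are counted in full although 83% to 97% of them would have run out before index at 30 to 5 days supplied.

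The actual size cannot be known from the document, because it gives neither fill rates nor the share of one-off users. A recency condition reduces the artefact (16% to 48%) without removing it, so neither the present nor the restricted proportion should be read as an effect of rimegepant by itself.

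**What to change.** 1. Relabel the present measure as no post-index fill in Section 8.1, Table 1, Table 2 and Section 8.7.1, and treat it as descriptive.
2. Report discontinuation among patients with at least one fill of the drug in W4-W6, keeping the 180-day outcome (no fill in W7-W12).
3. In each medication group, tabulate as a no-effect benchmark the W1-W3 users with no W4-W6 fill beside the W4-W6 users with no W7-W9 fill. State that the two agree only if use is stable before index, that a rise just before index produces a spurious difference, and that the difference is therefore supportive and not a drug effect.
4. If the data dictionary already holds an active-use rule, reconcile it with Section 8.1 and Table 1.

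The cost is wording and extra tabulations from the W1-W12 file already planned; no new data are needed. The restricted denominator loses 22% to 40% of entrants under the assumed model, and the reported proportion is likely to be smaller. The Abstract states that analyses were completed in 2024, so the added tabulations must be labelled post hoc.
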